### 7.6.2. Treatment Compliance

Percent compliance will be listed for each patient and summarized by treatment on the safety population. Percent compliance and treatment compliance will be summarized by treatment for each period and by treatment only.

Percent compliance will be calculated for each subject as

$$\frac{(\text{Number of injections administered [regardless of actual dose in mg administered]} \div \text{total number of injections expected to be administered}) \times 100}{}$$

Patients will be considered treatment compliant if taking 75% or more of their scheduled doses for the 6-week treatment period, considering early termination (specifically excluding the period after early termination).

## 7.7. Important Protocol Deviations

Important protocol deviations are defined as deviations from the study protocol that may significantly compromise the data integrity and/or patient safety. The details of identification of IPDs are provided in a separate document (that is, Risk and Issue Mitigation and Management Tool [RIMM]). A listing/table of IPDs will be provided by the study manger after database lock.

## 7.8. Pharmacokinetic Analyses

### 7.8.1. Pharmacokinetic Parameter Estimation

Sparse PK samples will be collected across the 6-week treatment period. Tirzepatide concentrations will be determined to support an understanding of tirzepatide exposure over the treatment duration and compare with expected tirzepatide PK.

### 7.8.2. Pharmacokinetic Statistical Inference

No summaries or analyses of PK parameters are planned. Tirzepatide concentrations may be summarized by week.

## 7.9. Pharmacodynamic Analyses

### 7.9.1. Pharmacodynamic Parameter Estimation

Pharmacodynamic parameters will be measured at lead-in (baseline), Week 3, and/or Week 6, to assess the effect of study treatments on measures of appetite and food intake, food intake-related and impulsiveness questionnaires, central reward and appetite circuits in the brain, and hormones and metabolites related to appetite regulation. The change from baseline to Week 3 and Week 6 (if applicable) will be calculated for all continuous PD parameters.

**Table GPHH.7.2. Study Period and PD Measurements**

	Period	Visit (Study Day)	Week	PD Measurements
1	Lead-in (baseline)	2 (between Day -4 and Day -1)	-1	
 
Ad-libitum food intake test at lunch (clinic-based) with appetite VAS
 
FCI, FCQ-S, Eating Inventory, BIS and Power of Food Scale questionnaires
 
Retrospective appetite VAS
 
BOLD fMRI
 
Hormones and metabolites for appetite and metabolism regulation in the fasting and postprandial states
 

2	Treatment	6 ( $16 \pm 1$ )	Week 3	
 
Ad-libitum food intake test at lunch (clinic-based) with appetite VAS
 
FCI, FCQ-S, Eating Inventory, BIS and Power of Food Scale questionnaires
 
Retrospective appetite VAS
 

	Period	Visit (Study Day)	Week	PD Measurements
				
 
BOLD fMRI
 
Hormones and metabolites for appetite and metabolism regulation in the fasting and postprandial states
 

3	Treatment	11 (37 ±1)	Week 6	
 
Ad-libitum food intake test at lunch (clinic-based) with appetite VAS
 
FCI, FCQ-S, Eating Inventory, BIS and Power of Food Scale questionnaires
 
Retrospective appetite VAS
 
BOLD fMRI
 
Hormones and metabolites for appetite and metabolism regulation in the fasting and postprandial states
 

4	Follow-up	12 (59 ±1 if TZP or placebo and 61 ±1 if liraglutide)	Follow-up Week 3	
 
Ad-libitum food intake test at lunch (clinic-based)
 

5	Follow-up	All days between 12 and 13 (~4 days)		
 
Ad-libitum food intake assessment (free-living)
 

6	Follow-up	13 (64 ±1 if TZP/ or placebo and 66 ±1 if liraglutide)	Follow-up Week 4	
 
Ad-libitum food intake test at lunch (clinic-based)
 

Abbreviations: ~ = approximately; BIS = Barratt Impulsiveness Scale; BOLD = blood-oxygenation-level-dependent; FCI = Food Craving Inventory; FCQ-S = Food Craving Questionnaire-State; fMRI = functional MRI; MRI = magnetic resonance imaging; PD = pharmacodynamics; TZP = tirzepatide; VAS = visual analog scale.

### 7.9.1.1. Food Intake (Ad-Libitum Food-Intake Test)

Food intake will be quantified through an ad-libitum food-intake test at lunch in a clinical setting and in free-living conditions on baseline (measured in the lead-in period between Day -4 to Day -1), treatment Week 3 (Visit 6, Day 16) and Week 6 (Visit 11, Day 37), and during the follow-up period specified in the above table.

### 7.9.1.2. Central Reward and Appetite Circuits using BOLD fMRI

To characterize the treatment effect on central reward and appetite circuits in the brain, MRI scans will be completed during the study. In particular, BOLD fMRI will be completed by subjects at lead-in (measured between Day -4 to Day -1) and treatment Week 3 (Visit 6, Day 16) and Week 6 (Visit 11, Day 37), respectively.

On each of the 3 scheduled visits, 1 MRI scan session will be completed in a fasted state. Subjects will perform a food image task during each scan.

The principal brain reward and appetite areas to be examined will be the

- insula

- medial frontal gyrus
- superior temporal gyrus
- precentral gyrus, and
- cingulate gyrus.

In addition, exploratory brain reward and appetite areas to be examined will be the

- hippocampus
- putamen
- orbitofrontal cortex, and
- ventral striatum.

#### **7.9.1.3. Appetite Visual Analog Scale and Retrospective Appetite Visual Analog Scale**

The aim of the appetite VAS is to determine the effects of study treatments on appetite sensations and desire for specific foods. Two types of VASs will be used to assess subjective ratings of appetite and affect: laboratory-based and retrospective. The VASs will be analyzed as continuous variables on the 0 to 100 scale for individual components.

Visual analog scale scores will be documented in an electronic clinical report form (eCRF). During the laboratory-based test meals at baseline (that is, lead-in, measured between Day -4 to Day -1), Week 3, and Week 6, subjects will complete pen-and-paper VAS ratings immediately before and after the test lunch and document scores in the eCRF.

#### **7.9.1.4. Measures of Food Intake-Related and Impulsiveness Questionnaires**

The FCI, FCQ-S, Eating Inventory (also known as the TFEQ), Power of Food Scale, and BIS questionnaires are administered at baseline (measured in the lead-in period between Day -4 to Day -1), Week 3, and Week 6 postprandially and will be documented in the eCRF.

##### **Food Craving Inventory**

The 33-item FCI (White et al. 2002) will be used to measure cravings for specific food groups. The measure consists of 5 empirically derived factors. The FCI will be completed at baseline (measured in the lead-in period between Day -4 to Day -1), Week 3, and Week 6 in a fasted state shortly after arriving to the study site and will be documented in the eCRF.

##### **Food Craving Questionnaire-State**

The FCQ-S (Cepeda-Benito et al. 2000; Moreno et al. 2008) is a 15-item measure that assesses the strength of state food cravings at the moment of administration. All items are scored using a 5-point Likert scale in the following manner:

- Strongly disagree - (1).
- Disagree - (2).
- Neutral - (3).
- Agree - (4).
- Strongly agree - (5).

Greater scores for each subscale denote higher levels of craving.

The FCQ-S will be completed at baseline (measured in the lead-in period between Day -4 to Day -1), Week 3, and Week 6 in a fasted state shortly after arriving to the study site and will be documented in the eCRF.

### **Eating Inventory**

The Eating Inventory (Stunkard and Messick 1985; Stunkard and Messick 1988) or the TFEQ is a 51-item, validated questionnaire that assesses 3 eating-related constructs:

- dietary restraint (21 items)
- disinhibition (16 items), and
- perceived hunger (14 items).

Dietary restraint refers to the intent and ability to restrict food intake, disinhibition measures the tendency to overeat, and perceived hunger measures susceptibility to feelings of hunger.

Different items have different scales. The TFEQ will be completed at baseline (measured in the lead-in period between Day -4 to Day -1), Week 3, and Week 6 and will be documented in the eCRF.

### **Power of Food Scale**

The 21-item Power of Food Scale (Cappelleri et al. 2009; Lowe et al. 2009) measures appetite for palatable foods. Among 21 items, 15 items are used to calculate the subdomain scores at the following 3 levels of food proximity (3 domain scores):

- food available (6 items)
- food present (4 items), and
- food tasted (5 items).

The Power of Food Scale will be completed at baseline (measured in the lead-in period between Day -4 to Day -1), Week 3, and Week 6 and will be documented in the eCRF.

### **Barratt Impulsiveness Scale**

Impulsivity will be measured with the BIS. The BIS (Patton et al. 1995; Reid et al. 2014) is a 30-item, self-reported measure describing impulsive or nonimpulsive behaviors and preferences.

The BIS will be completed at baseline (measured in the lead-in period between Day -4 to Day -1), Week 3, and Week 6 in a fasted state shortly after arriving to the study site and will be documented in the eCRF.

#### **7.9.1.5. Hormones and Metabolites Related to Appetite Regulation**

To explore potential effects of study treatment on hormones related to appetite and the regulation of nutrient metabolism, plasma or serum samples will be collected and assayed. The following hormones measured at baseline (measured in the lead-in period between Day -4 to Day -1), Week 3, and Week 6 at a central laboratory will be exploratory PD parameters of interest and will be only tested once from either plasma or serum:

- amylin (postprandial)
- ghrelin (fasting)
- GIP (postprandial)
- GLP-1 (postprandial)
- leptin (postprandial)
- pancreatic polypeptide (postprandial)
- PYY (postprandial)
- insulin (fasting and postprandial), and
- glucagon (fasting).

In addition to safety monitoring, the following metabolites will also be measured as exploratory endpoints at baseline (Day -4; local laboratory), Week 3 (central laboratory), and Week 6 (central laboratory):

- plasma glucose (fasting), and
- triglycerides (fasting).

Glucose and triglycerides do not have central laboratory measures at baseline, so local laboratory measures will be used for baseline.

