## **7.9.2. Pharmacodynamic Statistical Inference**

Pharmacodynamic parameters at baseline (measured in the lead-in period between Day -4 to Day -1), Week 3, and Week 6 (if applicable), as well as change from baseline values at Week 3 and Week 6 and change from Week 3 at Week 6, will be summarized by treatment. Plots of mean PD parameters and mean changes from baseline over time may be provided by treatment and by time (that is, Week) if deemed necessary. The change from baseline to Week 3 and Week 6 (if applicable), calculated for all the continuous PD parameters, will be analyzed.

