### **7.9.2.2. Secondary Pharmacodynamic Analyses**

Secondary PD measures (that is, BOLD fMRI activation; VAS; and the FCI, FCQ-S, TFEQ, and Power of Food Scale questionnaires [see Section 7.10.1 for details]) are scheduled to be measured twice postbaseline at Week 3 and Week 6.

The PD measurements will be analyzed using a MMRM method to compare the effect of tirzepatide versus placebo at Week 3. The response variable is change from baseline in the PD measurement (that is, postbaseline - baseline), where postbaseline measurement is collected at Week 3 and Week 6. The model will include treatment, baseline BMI stratum, week, and treatment-by-week interaction as fixed effects and baseline PD measurement as a covariate; scanner ID will be included as a covariate for modelling the function MRI parameters as well. An unstructured covariance structure will be used to model the within-subject variabilities if deemed appropriate. The restricted-maximum-likelihood approach will be used to obtain model parameter estimates.

For both secondary and exploratory PD parameters, a single model for each parameter will be constructed. The inferential results will be displayed into section for secondary endpoints and section for exploratory endpoints, separately.

For secondary endpoints, inferential statistics will include LSMs (Standard error) of each treatment, the treatment difference with 95% CI at Week 3, along with the p value for comparison.

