### **Hormones and metabolites related to appetite regulation**

To explore potential effects of study treatment on hormones related to appetite and the regulation of nutrient metabolism, plasma or serum samples will be collected and assayed. The following hormones measured at baseline, Week 3, and Week 6 at a central laboratory will be exploratory PD parameters of interest and will be only tested once from either plasma or serum:

- amylin (postprandial)
- ghrelin (fasting)
- GIP (postprandial)
- GLP-1 (postprandial)
- leptin (postprandial)
- pancreatic polypeptide (postprandial)
- PYY (postprandial)
- insulin (fasting and postprandial), and
- glucagon (fasting).

In addition to safety monitoring, the following metabolites will also be measured as exploratory endpoints at lead-in (Day -4; local laboratory), Week 3 (central laboratory), and Week 6 (central laboratory): plasma glucose (fasting) and triglycerides (fasting). Note that glucose and triglycerides do not have central laboratory measures at baseline, so local laboratory measures will be used for baseline.

Exploratory PD measures to compare the effect of 5- and 10-mg tirzepatide versus placebo at Week 3 and Week 6 on hormones and metabolites related to appetite regulation are

- change from baseline to Week 3 and Week 6 in
  - ghrelin (fasting)
  - glucagon (fasting)
  - insulin (fasting and postprandial)
  - amylin (postprandial)
  - GIP (postprandial)
  - GLP-1 (postprandial)
  - leptin (postprandial)
  - pancreatic polypeptide (postprandial), and
  - PYY (postprandial)
- change from baseline to Week 3 and Week 6 in plasma glucose (fasting) and triglycerides (fasting).

Exploratory PD measures to compare the effect of 5-mg and 10-mg tirzepatide versus liraglutide, and liraglutide versus placebo, at Week 3 and Week 6 on hormones and metabolites related to appetite regulation are

- change from baseline to Week 3 and Week 6 in
  - ghrelin (fasting)
  - glucagon (fasting)
  - insulin (fasting and postprandial)
  - amylin (postprandial)
  - GIP (postprandial)
  - GLP-1 (postprandial)
  - leptin (postprandial)
  - pancreatic polypeptide (postprandial), and

- PYY (postprandial)
- change from baseline to Week 3 and Week 6 in plasma glucose (fasting) and triglycerides (fasting).

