Hormone and metabolites analyses are considered as exploratory analyses only. The estimand is pairwise treatment difference in terms of change from baseline to treatment Week 3 and 6. In particular, interest lies in comparing tirzepatide 5 mg with liraglutide, tirzepatide 10 mg with liraglutide, and liraglutide with placebo. All 11 variables described above will be analyzed separately using an MMRM model.

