### Summary for PD analysis

For PD analyses, when the distribution of response variables significantly deviates from normality, alternative statistical methods will be utilized.

Guided by results, for BOLD fMRI, additional analyses on parameters of central reward and appetite circuits using other functional contrasts (for example, highly palatable foods versus not highly palatable foods, not highly palatable foods versus nonfood objects) may be conducted at the 5 principal food-reward and appetite-related ROI and 4 exploratory food-reward and appetite-related ROI as deemed appropriate.

Inferential statistics will include LSMs of each treatment, the treatment difference, standard error, and 95% CI.

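### Glucose and triglyceride change from baseline crosses from local to central laboratories, so each arm's own change, though not the between-arm difference, carries any laboratory offset

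*SAP*

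**What the plan says.** SAP 7.9.1.5 takes baseline fasting glucose and triglycerides from a local laboratory and the Week 3 and Week 6 values from a central one: "Glucose and triglycerides do not have central laboratory measures at baseline, so local laboratory measures will be used for baseline". The hormones and metabolites part of SAP 7.9.2.3 repeats the rule.

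The protocol agrees. Appendix 4 lists two samples each for glucose and triglycerides, at Weeks 3 and 6 only, sent to a central or referral laboratory. The hormones have three. Safety laboratory tests are run on site or locally. Appendix 2, footnote a, has the two analytes assayed only once when efficacy and safety sampling coincide, as they do at Visit 2.

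For reporting, SAP 7.9.2 says that "change from baseline values at Week 3 and Week 6 and change from Week 3 at Week 6, will be summarized by treatment". The summary at the end of SAP 7.9.2.3 adds: "Inferential statistics will include LSMs of each treatment, the treatment difference, standard error, and 95% CI". The target for these analytes is stated as: "The estimand is pairwise treatment difference in terms of change from baseline to treatment Week 3 and 6". The model in SAP 7.9.2.2 contains "treatment, baseline BMI stratum, week, and treatment-by-week interaction as fixed effects and baseline PD measurement as a covariate", with scanner ID added for the fMRI parameters only.

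**The concern.** A change score is clean only if both readings are on the same scale. Here the earlier reading comes from one of possibly several local laboratories and the later one from the central laboratory. Any calibration difference therefore looks like a change over time. A table showing that fasting glucose fell by some amount on tirzepatide would mix drug effect with assay difference, and nothing in the table would tell the reader.

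The trial is multicenter, so local methods may also differ between sites. The SAP has no laboratory or site term for these analytes, no bridging step, no sensitivity analysis and no caveat. SAP section 9 does not mention the mismatch. The plan does deal with the same problem in imaging: scanner ID is a covariate, and protocol Appendix 5 adds a hand-squeeze task to evaluate inter-scanner variability.

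**Working it through.** **Algebra.** Let b be the central reading minus the local reading for the same blood. The local baseline is then the baseline on the central scale minus b, so

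observed change = follow-up - (baseline - b) = true change + b.

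This holds in every arm at Week 3 and at Week 6, for raw means and for LS means of change. For the difference between two arms:

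(change in arm 1 + b) - (change in arm 2 + b) = change in arm 1 - change in arm 2.

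Baseline is taken on Day -4 to Day -1, before randomization on Day 1. Offsets that differ by site are therefore balanced across arms in expectation and cause no bias.

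**Illustration for glucose.** The documents give no offset, no variance for these analytes and no number of sites, so every input except 31 completers per arm (protocol 10.1) is assumed: true change 0 on placebo and -5 mg/dL on tirzepatide; baseline mean 95, between-subject SD 8, reading SD 4; follow-up regressing on true baseline with slope 0.8. The analysis is a single-visit ANCOVA with baseline as covariate, a simplification of the planned MMRM, over 3,000 simulated trials per row.

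| Assumed b (mg/dL) | Placebo change | Tirzepatide change | Adjusted difference |
|---|---|---|---|
| -5 | -4.99 | -10.02 | -5.02 |
| -2 | -2.02 | -7.02 | -4.98 |
| 0 | 0.02 | -4.99 | -5.00 |
| +2 | 2.01 | -3.00 | -4.99 |
| +5 | 5.02 | 0.01 | -5.01 |

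The arm changes move one-for-one with b, and the difference does not move. At b = +5 a real fall of 5 reads as no change.

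**Offsets that vary by site.** With an assumed between-site SD of 3 mg/dL and 4 sites, the difference stays between -4.95 and -5.04. Its standard error rises from 1.22-1.27 to 1.30-1.34, or from about 1.25 to about 1.32 (1.32/1.25 = 1.06, some 6%). The sampling SD of the placebo arm's mean change rises more, from 1.04-1.07 to 1.85-1.91.

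No triglyceride figures were run. The algebra is the same, with b in triglyceride units.

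**Blood volume.** The Appendix 4 rows, optional samples included, are 24 + 90 + 24 + 6 + 6 + 4 + 5 + 7.5 + 7.5 + 15 + 15 + 12 + 6 + 15 + 70 + 10 + 33 = 350 mL, which matches the stated total. A newly drawn central baseline for both analytes would add 2 + 2.5 = 4.5 mL, giving 354.5 mL.

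**The case against.** The strongest reply is that the planned inference is sound. The estimand is the pairwise treatment difference, and a common offset cancels from it. The placebo arm exists to expose study conditions, and a laboratory offset is one of them. This stands. A reader might infer that the estimated tirzepatide effect on glucose or triglycerides is biased, but the documents do not support that.

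A reader might also infer that every within-arm glucose or triglyceride change in the report is contaminated. That is not so either:

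- The change from Week 3 to Week 6 is central at both ends.
- The safety chemistry in SAP 7.10.6 summarizes change from baseline by visit and arm. The tests include fasting glucose and triglycerides (protocol Appendix 2), are run on site or locally (Appendix 4), and fall at Visit 2 and Day 36. A local-to-local change near Week 6 is therefore already planned, though none at Week 3.

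The arrangement is also deliberate and disclosed: it follows from the single-assay rule in Appendix 2 and is stated twice in the SAP. Disclosing the source of the baseline does not, however, warn the reader of a table of arm changes.

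Finally, a new central baseline draw is probably too late. The SAP is at version 3, follows a blinded review of fMRI data, and states as fact that no central baseline exists. This also stands, and it makes the SAP-only remedy the main one.

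**Conclusion.** The point holds for the exploratory change from baseline in fasting glucose and triglycerides at Weeks 3 and 6. Each arm's descriptive change and LS mean change contains the whole central-minus-local offset. The size and sign of that offset are unknown and it may be near zero; the range of -5 to +5 mg/dL is an assumption, and the plan includes no step to find out.

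The between-arm difference is unbiased. Site-varying offsets cost it a little precision, about 6% in standard error under the assumed 4 sites and SD of 3 mg/dL. Both analytes are exploratory, and the primary endpoint, secondary endpoints and sample size are untouched. This is a minor reporting point, worth correcting because it is cheap and stops a laboratory difference being read as a drug effect.

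**What to change.** In the SAP, for glucose and triglycerides only:

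1. Add local laboratory (or site) as a covariate in the MMRM, as scanner ID is for fMRI. This absorbs noise between laboratories; it does not remove b from the arm means.
2. Base inference on between-arm differences only.
3. Do not interpret the within-arm change from baseline as a drug effect. Either omit its LS means, or flag them as crossing laboratories and direct the reader to the local-to-local Day 36 safety change for a within-arm estimate near Week 6.

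Recasting the outcome as the Week 3 or Week 6 value is unnecessary: with baseline as a covariate the treatment difference is identical.

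The cost is a few degrees of freedom and no clean within-arm change at Week 3. The Day 36 local and Day 37 central values would allow a rough look at the offset, although they are a day apart and, in the weekly arms, may be separated by a dose.

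Only if baseline sampling is still open, or suitable fasting baseline sample remains, should baseline be assayed centrally. A new draw adds 4.5 mL (354.5 mL in total). Appendix 2, footnote a, and Appendix 4 would have to be amended to match.

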## **7.9.2. Pharmacodynamic Statistical Inference**

Pharmacodynamic parameters at baseline (measured in the lead-in period between Day -4 to Day -1), Week 3, and Week 6 (if applicable), as well as change from baseline values at Week 3 and Week 6 and change from Week 3 at Week 6, will be summarized by treatment. Plots of mean PD parameters and mean changes from baseline over time may be provided by treatment and by time (that is, Week) if deemed necessary. The change from baseline to Week 3 and Week 6 (if applicable), calculated for all the continuous PD parameters, will be analyzed.

